This study will be a controlled trial of the two standard of care methods of securing SCS leads in which the trial leads (left and right) will be secured with 1 lead being secured with a suture only while the 2nd lead will be secured after placement with both a suture in addition to Dermabond. All other factors in the SCS trial lead placement will be unaffected by this study. In this manner, the patient will serve as their own control. This will limit confounding factors between patients that may predispose them to migration based on body habitus, sheer forces of back musculature, and other physical attributes that could augment lead migration. In the standard of care SCS 'trials', one lead is typically place to the left of midline (1-2 cm from midline), and another lead to the right of midline (1-2 cm from midline). Although, the anatomy of the two placement location should be identical, we will randomize which lead (left or right) in each patient gets suture plus Dermabond versus suture only to limit any potential procedural (though unlikely) bias in which SCS lead gets secured in a certain fashion. This is within participant randomization. Demographics of the subject to be retrieved include the following: Age, BMI, height, weight, race, ethnicity, history of spine surgery, sex at birth. We will also collect the radiological information required to meet the study objective of this protocol.

As is the standard of care with this subject population, once procedure is completed on Day 0, the patient will be sent for X-ray imaging right after the trial as well as between days 5-8 post procedure. During this second X-ray, the placement of the leads will be evaluated by measuring the amount of lead migration by a physician not involved in the trial. Lead migration will be measured in millimeters from original placement on X-ray imaging. Of note, imaging is obtained during the placement of the trial leads via fluoroscopy. Depending on the location,

the post trial images may be done via x-ray imaging or via fluoroscopy. Either radiological studies are acceptable methods to be used in the analysis of lead migration for this study. The average and median mm of migration per trial will be compared between the two mechanisms of securing the lead. The rate of migration is defined as greater than 4 mm between the two groups. Patient satisfaction survey will also be reviewed upon lead removal by a member of the study team.

Setting

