This will be a single center, academic setting at Atrium Wake Forest Baptist with the Pain Service Line.

Subjects selection criteria

- **Inclusion Criteria**

Any patient presenting to the Pain Service Line for SCS 'trial' lead placement in the thoracic spine defined as terminal tip end in the thoracic spine.

- **Exclusion Criteria**

Allergy to Dermabond and/or Suture material.

Inability to place two leads in the patient.

Lead placement outside of the thoracic spine

- **Sample Size**

Assuming the mean lead migration for use of Dermabond is 2.49 mm compared to mean non-Dermabond usage of 3.24mm, with variance of 1mm, total sample size need for study with study power of 80% with 95%CI for 2-tail test is 56 for both the groups. Lead migration is estimated to occur at a rate of about 13.2% and this number would provide enough analysis to determine if there is a difference in the rates of migration between the groups. No interim analysis will be performed as there is no potential significant harm to the patient and both approaches are standard of care.

Outcome Measure(s)

- **Primary Outcome Measure**

Migration rate of trial leads anchored with Dermabond + suture versus suture alone.

- **Title:** Migration rate of trial leads anchored with Dermabond + suture versus suture alone
- **Description:** Change in 'trial' lead position as measured in millimeters when comparing initial x-ray after placement versus x-ray taken at lead removal 5-8 days after placement.
- **Time Frame:** 5-8 days after placement of trial lead

- **Secondary Outcome Measure**

- **Title:** Number of patients who received pain relief from the SCS 'trial'
- **Description:** Number of responders to the prognostic lead placements defined as >50% pain relief over the length of the trial.
- **Time Frame:** 5-8 Days after placement of trial leads

- **Secondary Outcome Measure**

- **Title:** Patient satisfaction
- **Description:** Lower satisfaction in patients that had lead migration versus patients that did not
- **Time Frame:** 5-8 Days after placement of trial leads

- **Secondary Outcome Measure**

- **Title:** Effect of length of trial on migration
- **Description:** Does a longer trial predispose to a higher rate of infection within a 5-8 day period
- **Time Frame:** 5-8 Days after placement of trial leads

- **Secondary Outcome Measure**

- **Title:** Prone fluoroscopy vs upright PA x-ray

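### The statement that 56 is enough to compare migration rates at 13.2% rests on no rate calculation, and power for that comparison is low under most plausible assumptions

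*Combined protocol and SAP*

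**What the plan says.** The Sample Size section of the combined protocol and SAP takes its figures from means alone: "Assuming the mean lead migration for use of Dermabond is 2.49 mm", "compared to mean non-Dermabond usage of 3.24mm", "with variance of 1mm", "study power of 80% with 95%CI for 2-tail test". The result "is 56 for both the groups". The next sentence turns to rates: "Lead migration is estimated to occur at a rate of about 13.2" per cent, and "this number would provide enough analysis to determine if there is a difference in the rates of migration between the groups". The 13.2% is not assigned to either securing method.

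Elsewhere, Interventions and Interactions sets the event threshold: "The rate of migration is defined as greater than 4 mm between the two groups". The same section randomises the two leads within each patient. Under Outcome Measure(s), the primary outcome is titled as a migration rate but described as a change in position in millimetres. The Analytical Plan names chi-square tests for proportions and no paired test.

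**The concern.** A sample size derived for a continuous outcome does not automatically serve a binary one, least of all when events are uncommon. At 13.2%, the expected number of migrated leads in an arm is 28 × 0.132 = 3.7, or 56 × 0.132 = 7.4. Few contrasts can be resolved with so few events.

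The rate appears in the title of the primary outcome, so this is not a peripheral comparison. A reader who trusts the Sample Size section would take a non-significant rate comparison as evidence that the two methods perform alike, when the study would usually have missed even a large difference.

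**Working it through.** **1. The plan's own figure.** Inputs from Sample Size: difference 3.24 − 2.49 = 0.75 mm; variance 1, so SD 1 mm; two-sided 5%; 80% power.

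n per group = 2 × (1.960 + 0.842)² × 1² / 0.75² = 27.9, rounded up to 28, or 56 in total. The stated 56 is reproduced for the means. (A t-based calculation gives 28.9 per group, 58 in total.)

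Read literally, 56 is the total, or 28 leads per arm. Because each patient contributes one lead to each arm, it could also mean 56 patients and 56 leads per arm. Both are carried below.

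**2. Rate comparison, base case.** The documents state no effect on the rate. Assume that 13.2% is the suture-only rate and Dermabond halves it to 6.6%, so the difference is 0.066 and the mean rate 0.099.

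z = [0.066 × √n − 1.960 × √(2 × 0.099 × 0.901)] / √(0.132 × 0.868 + 0.066 × 0.934) = (0.066 × √n − 0.828) / 0.420

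- n = 28: (0.349 − 0.828) / 0.420 = −1.14, power 12.7% (13.2% by exact enumeration of Pearson chi-square).
- n = 56: (0.494 − 0.828) / 0.420 = −0.80, power 21.3% (same by enumeration).
- For 80%: n = (0.828 + 0.842 × 0.420)² / 0.066² ≈ 320 per arm (321 after rounding up).

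**3. Paired tests.** McNemar power was enumerated over within-patient correlation on a latent normal scale from 0 to 0.8. For the halving, the exact test gives 2–4% with 28 pairs and 13–16% with 56. With 56 pairs, mid-p gives 19–27% and the uncorrected test 19–34%. At the mathematical limit of correlation, the uncorrected test reaches about 51%, but discordant pairs are then too few for its approximation to be trusted.

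**4. Complete elimination (13.2% vs 0).** Every discordant pair then favours Dermabond. Exact McNemar needs at least 6 of them (2 × 0.5⁶ = 0.031, whereas 2 × 0.5⁵ = 0.0625). Pearson needs at least 4 events against none. The binomial probabilities of reaching those counts are 16% and 52% with 28 leads, and 77% and 95% with 56.

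**5. Rates implied by the plan's means.** With normal distributions, SD 1 and the 4 mm threshold: P(Z > (4 − 3.24)/1) = P(Z > 0.76) = 22.4% and P(Z > (4 − 2.49)/1) = P(Z > 1.51) = 6.6%.

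**Power at two-sided 5%:**

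| Suture only vs Dermabond + suture | 28 per arm: Pearson | 28 pairs: exact McNemar | 56 per arm: Pearson | 56 pairs: exact McNemar |
|---|---|---|---|---|
| 13.2% vs 6.6% | 13% | 2–4% | 21% | 13–16% |
| 13.2% vs 3.3% | 26% | 6–8% | 49% | 34–43%* |
| 13.2% vs 0% | 52% | 16% | 95% | 77% |
| 22.4% vs 6.6% | 41% | 23–27% | 69% | 58–83% |

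*Correlation 0 to 0.7.

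For 22.4% vs 6.6% with 56 pairs, mid-p and uncorrected McNemar give 67–91%, rising with correlation. With 28 pairs, all three paired tests together span 23–60%.

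**The case against.** The plan never says which rate difference it expects, nor to which arm 13.2% belongs, so the halving is supplied from outside. That is correct. A reader might go further than the documents allow in three ways.

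- **That the sentence is shown to be false.** Without a stated effect it has no definite content to refute. What can be shown is that nothing supports it.
- **That 80% power requires Dermabond to abolish migration.** It does not. With 56 pairs and the rates implied by the plan's own means, exact McNemar reaches 83% at a latent correlation of 0.8, and mid-p and uncorrected tests go higher. The protocol justifies the own-control design by shared patient factors, so positive correlation is plausible, although no value is given.
- **That 21% is a ceiling for a halving.** It is the figure for unpaired Pearson chi-square with 56 per arm; some paired tests exceed it.

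Also, if 13.2% were the Dermabond rate (26.4% vs 13.2%), power would be better: 43% by Pearson with 56 per arm, and 33–58% by exact McNemar. That is still short of 80%.

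Finally, the primary outcome is described in millimetres. On that reading the study is sized for its primary endpoint and the disputed sentence is a side remark. This lowers the stakes but does not settle the matter, because the outcome's title says rate.

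**Conclusion.** The point stands as an unsupported statement of adequacy. The 56 is not itself an arithmetic error: it reproduces, for means only.

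For a halving from 13.2%, power is 13% or 21% with Pearson chi-square, the test family the plan names, and at most about 34% by any paired test examined at latent correlations up to 0.8. With 28 leads per arm, the literal reading, not even complete elimination from 13.2% gets beyond 52%. With 56 pairs, 80% comes within reach only under near-complete elimination, or under the normal-theory rates of 22.4% vs 6.6% combined with high within-patient correlation. Neither is stated or justified in the plan.

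These figures assume that 13.2% is the suture-only rate (except where 22.4% is used) and that no patient is lost. The plan states no dropout allowance, and losses would lower power further.

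**What to change.** Delete the sentence on rates in Sample Size. State instead that the study is sized for mean migration in millimetres and is not powered to detect a difference in the proportion of leads migrating more than 4 mm, which will be reported as a paired difference with a 95% confidence interval.

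Two other places must change with it, or the plan will contradict itself:

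- **Outcome Measure(s):** reconcile the primary outcome's title with its millimetre description, for example by titling it mean migration in millimetres and listing the proportion above 4 mm as a secondary outcome.
- **Analytical Plan:** name a paired analysis for that proportion in place of the general chi-square test.

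The choice of primary endpoint is the sponsor's. If the rate is intended, both rates and the within-patient correlation have to be stated and the study re-sized.

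For the first course, the cost is a few lines of text and a less favourable description of what the study can show. No extra patients are needed.

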The suture is a silk sterile surgical suture material. Dermabond is a quick drying adhesive that is currently utilized for assisting in the closure of medical incisions with minimal risk. The use of Dermabond has not been formally investigated but is in common use for securing SCS 'trial' leads. It is unknown which standard of care mechanism of securing SCS trials leads is superior in reducing lead migration. One may be more effective alternative to decrease the incidence of such lead migration, thereby allowing for improvement of outcomes during spinal cord stimulation trial lead placement (in anticipation of surgical placement of spinal cord stimulators for the treatment of chronic pain).

Objectives

Main objective

Determine if the use of Dermabond plus suture as compared to suture alone at the insertion site of a trial spinal cord stimulator lead will lead to less lead migration at the end of the trial period (typically 5-8 days).

Additional Objectives

1. Assess if lead migration changes effectiveness of 'trial'
2. Compare patient satisfaction between patients with migration and without

3. Assess trial lengths effects 5 versus 6 versus 7 versus 8 days on lead migrations rates
4. Determine if there is a change in lead position when using Dermabond plus suture vs suture alone when laying prone on the operating table and then standing and having a PA x-ray performed with radiology

Methods and Measures

Design

All patients who are being considered for a permanent spinal cord stimulator placement are required to have spinal cord stimulator 'trial' leads placed to ensure they are an appropriate candidate for treatment with this device. These trial leads are placed by pain medicine physicians in the pain centers and are secured with either tape and suture, or tape and a combination of Dermabond with suture. Security is at the discretion of the inserting physician. Currently it is not known which method is the best method of securing trial leads to prevent lead migration.

Interventions and Interactions

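### The primary outcome is titled as a migration rate but described and sized in millimetres, and the claim that 56 is also enough for rates is unsupported

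*Combined protocol and SAP*

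**What the plan says.** Under Outcome Measure(s) there is one primary outcome. Its title is "Migration rate of trial leads anchored with Dermabond + suture versus suture alone". Its description, directly below, is "Change in 'trial' lead position as measured in millimeters when comparing initial x-ray after placement versus x-ray taken at lead removal 5-8 days after placement".

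The Interventions and Interactions section gives two further statements: "The rate of migration is defined as greater than 4 mm between the two groups" and "The average and median mm of migration per trial will be compared between the two mechanisms of securing the lead". The main objective speaks only of less migration and names no scale.

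The Sample Size section works on means: "Assuming the mean lead migration for use of Dermabond is 2.49 mm compared to mean non-Dermabond usage of 3.24mm, with variance of 1mm", from which "total sample size need for study with study power of 80% with 95%CI for 2-tail test is 56 for both the groups". It then puts the migration rate at about 13.2% and says that the same number is enough to find a difference in rates. It gives no second rate, no effect size and no power for that comparison.

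The Analytical Plan lists chi-square tests for proportions and t-tests or ANOVA for continuous variables. It does not tie either to the primary outcome, names no test for medians and sets no order among results.

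**The concern.** The title and the description of one outcome ask for different variables: a yes/no event per lead (more than 4 mm), or a distance per lead. They need different tests and have very different power at the same sample size. If the two disagree, nothing in the plan says whether the trial has shown a difference. A reader would also take the Sample Size section to mean that both scales are adequately covered, so a non-significant rate could be misread as evidence that the two methods migrate equally often.

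**Working it through.** **1. Reproduce the plan's figure.** Inputs from the Sample Size section: difference 3.24 − 2.49 = 0.75 mm, variance 1 (SD 1 mm), two-sided 5%, 80% power.

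n per group = 2 × SD² × (1.960 + 0.842)² / 0.75² = 2 × 7.849 / 0.5625 = 27.9, so 28 per group and 56 in total.

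This matches exactly. It is a comparison of two independent means, so the powered quantity is mean millimetres. The text does not say whether 56 counts leads (28 patients) or patients, so both readings are carried below.

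**2. Power in millimetres, paired.** The SD of the within-patient difference is √(2(1 − ρ)), where ρ is the correlation between a patient's two leads. The documents do not give ρ; 0 and 0.5 are assumed, giving SDs of 1.414 and 1. The noncentral t distribution gives the first row of the table in step 4.

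**3. Rates implied by the plan's means and variance.** Assuming normality, which the plan does not state:

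- suture only: 1 − Φ(4 − 3.24) = 1 − Φ(0.76) = 22.4%
- Dermabond plus suture: 1 − Φ(4 − 2.49) = 1 − Φ(1.51) = 6.6%

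**4. Power for the >4 mm rate.** Bivariate normal discordant probabilities (only the suture-only lead migrates; only the other lead migrates) are 0.209 and 0.051 at ρ = 0, and 0.185 and 0.027 at ρ = 0.5. Exact McNemar power is by enumeration. Chi-square power is by enumeration with leads treated as independent.

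| | 28 patients | 56 patients |
|---|---|---|
| Paired t-test, mm (ρ 0 to 0.5) | 77% to 97% | 97% to above 99% |
| Exact McNemar, >4 mm (ρ 0 to 0.5) | 23% to 26% | 58% to 69% |
| Chi-square, >4 mm | 41% | 69% |

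For 80% power with independent groups, n per group = [1.960√(2p̄(1 − p̄)) + 0.842√(p₁(1 − p₁) + p₂(1 − p₂))]² / (p₁ − p₂)², which gives 77 for 22.4% against 6.6%.

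**5. Start instead from the plan's only stated rate, 13.2%.** The comparators are assumptions. Chi-square power is by exact enumeration; n per group uses the formula in step 4.

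| 13.2% against | 28 leads per method | 56 leads per method | n per group for 80% |
|---|---|---|---|
| 6.6% | 13% | 21% | 321 |
| 3.3% | 26% | 49% | 121 |
| 0% | 52% | 95% (81% by normal approximation) | 55 |

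Exact McNemar power in the last case is 77% with 56 pairs.

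**6. How often would the two scales disagree?** The chance that the millimetre test is significant and the rate test is not is at least the difference of their powers. With McNemar at 28 patients this is at least 77 − 23 = 54% (ρ = 0) and 97 − 26 = 71% (ρ = 0.5). At 56 patients it is at least 97 − 58 = 39% (ρ = 0) and about 30% (above 99, minus 69; ρ = 0.5).

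**7. Error rate if the best of mean, median and rate were chosen, each at 5%.** Independence would give 1 − 0.95³ = 14.3%, but the three are correlated. Simulation gave 6–8% with paired tests. With unpaired tests it gave about 10% at ρ = 0 and about 3% at ρ = 0.5, where those tests are conservative.

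**The case against.** The best defence is that the plan does address rates, since it says the number is enough for them. That sentence is there and must be weighed, but it offers one rate and nothing to compare it with. The check supports it only in extreme cases with 56 patients. One is 13.2% against 0%, tested by chi-square. The other is 22.4% against 6.6% when each Dermabond migration falls in a patient whose suture-only lead also migrated; McNemar power is then 90%.

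A second defence is that rate is loose wording for amount. The 4 mm definition, and the separate discussion of rates in the Sample Size section, tell against this.

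Three stronger readings are tempting, and the documents do not support them.

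- A reader might infer three rival primary results: mean, median and rate. There is one primary outcome with two conflicting scales. Mean and median appear in the methods narrative, neither is labelled primary, and they can be read as two summaries of one variable. What is missing is the choice of summary.
- A reader might infer that the 5% error rate is lost. The inflation is modest with paired tests, absent in one unpaired case, and rests on a median test that the plan does not name. It is a secondary point.
- A reader might infer that unpaired tests are planned. The Analytical Plan says only t-tests, which does not exclude a paired one.

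It is also fair to say that the 22.4% and 6.6% rest on normality, which is doubtful for absolute distances. For that reason the 13.2% scenarios are shown as well. The precise power depends on these assumptions; the shortfall appears in nearly all of them.

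**Conclusion.** The point holds. One primary outcome carries two contradictory scales, with no named summary measure or deciding test, and the sample size supports only the difference in mean millimetres. The assertion that it also covers rates has no calculation behind it. Across the scenarios in the tables, the rate reaches 80% power only if Dermabond plus suture eliminates migration, there are 56 leads per method, and chi-square is used. Under the plan's own effect, with ρ from 0 to 0.5 and McNemar for the rate, a significant millimetre result with a non-significant rate is more likely than not with 28 patients, and has at least about a 30% chance with 56. The plan has no rule for that outcome. These figures assume normality, the stated correlations and, for the 13.2% scenarios, the comparators shown. The contradiction in the text depends on none of them.

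**What to change.** Before outcomes are seen:

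- Retitle the primary outcome as the mean within-patient difference (suture only minus Dermabond plus suture) in lead migration in millimetres at lead removal. Use absolute displacement so that upward and downward shifts do not cancel.
- Test it once, by a paired analysis at two-sided 5%. This is the scale on which 56 was calculated, and it suits the within-participant design.
- List the >4 mm rate, with a paired test, as secondary, and the median or signed-rank result as a sensitivity analysis.
- Delete the sentence saying that the number is sufficient for rates, or restate it with both rates, the test and the power.

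This needs a protocol amendment and no new data. The price is that the rate becomes secondary, which is a real choice because the present title and the Background both point to how often leads migrate. If the team prefers the rate as primary, the description must change to match, and the stated 80% power must be restated for a paired comparison of proportions, with the sample size revised if it falls short.

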- **Description:** Difference in lead position on prone fluoroscopy versus upright PA x-ray when comparing Dermabond plus suture versus suture only at lead insertion site
- **Time Frame:** 5-8 Days after placement of trial leads

Analytical Plan

Results will be analyzed initially using descriptive statistics. Comparison between groups will be done using chi square tests for proportions, and t-tests or ANOVA procedures for continuous variables. Regression analysis will be performed to identify independent outcome predictors. Other inferential statistical analysis will be conducted as appropriate.

Human Subjects Protection

Subject Recruitment Methods

All patients undergoing percutaneous SCS trial at Atrium Health - Wake Forest Baptist will be invited to participate in this study. All records will be kept in a secure locked location. Any electronic files will be maintained behind the medical center firewall with password protection. All information collected are de-identified without any patient specific information that can be identifiable to a particular patient.

If any collected patient identifying information corresponding to the unique study identifier will be utilized a linkage file will be stored separately from the data. The linkage file will be kept secure, with access limited to designated study personnel. Following data collection subject identifying information will be destroyed within 6 years.

Confidentiality will be protected by collecting only information needed to assess study outcomes, minimizing to the fullest extent possible the collection of any information that could directly identify subjects, and maintaining all study information in a secure manner. To help ensure subject privacy and confidentiality, only a unique study identifier will appear on the data collection form. Any collected patient identifying information corresponding to the unique study identifier will be maintained on a linkage file, store separately from the data. Data and records will be kept locked and secured, with any computer data password protected. No reference to any individual participant will appear in reports, presentations, or publications that may arise from the study.

Informed Consent

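### Objective 1 rests on a yes/no pain-relief count alone; percent relief should be recorded and analysed beside it

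*Combined protocol and SAP*

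**What the plan says.** Additional Objectives, item 1, reads "Assess if lead migration changes effectiveness of" the SCS trial. Under Outcome Measure(s), the matching secondary outcome is "Number of responders to the prognostic lead placements defined as >50% pain relief over the length of the trial". Patient satisfaction is a separate outcome and belongs to the second additional objective.

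The Analytical Plan is generic: "Comparison between groups will be done using chi square tests for proportions, and t-tests or ANOVA procedures for continuous variables". It adds "Regression analysis will be performed to identify independent outcome predictors" without naming the outcome or the model, and allows other inference as needed. No pain scale, continuous pain score or analysis of percent relief is named.

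The Sample Size section concerns millimetres of migration only. It gives no power, responder rate, standard deviation or effect size for pain relief.

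**The concern.** Once the cut is applied, a patient with 10% relief counts the same as one with 50%, and 51% counts the same as 100%. The percentage is needed to classify the patient but has no stated use afterwards. If relief varies smoothly and migration erodes it, a test on responder status is more likely than a test on the percentage to miss the effect.

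The Background motivates the study by saying that migration can make the SCS trial fail technically and raise false negatives. Objective 1 is where that link is examined. A non-significant chi-square result from a small comparison could be read as showing that migration does not matter to pain relief. If the percentage is not entered as a number at the time, it may not be recoverable later. The plan does not say in what form relief is recorded.

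This point is about the cut on pain relief, not the 4 mm cut on migration.

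**Working it through.** **The plan's own figure.** The Sample Size section assumes "mean lead migration for use of Dermabond is 2.49 mm compared to mean non-Dermabond usage of 3.24mm", variance 1, and states "study power of 80% with 95%CI for 2-tail test is 56 for both the groups". Per group, n = 2 × (1.960 + 0.842)² × 1 / 0.75² = 27.9, so 28 per group and 56 in total. The 56 reproduces, but for mean migration only.

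**Number of patients.** Each patient contributes two leads, so 56 could mean 56 patients or 56 leads (28 patients). Both are run.

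**Number migrated.** The Sample Size section puts migration at 13.2%.
- Per patient: 0.132 × 56 = 7.4, so 7 v 49; 0.132 × 28 = 3.7, so 4 v 24.
- Per lead, with independent leads and a patient counted if either lead moves: 1 − (1 − 0.132)² = 24.7%, so 14 v 42 or 7 v 21.

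**Assumptions not in the documents.** Relief is normal with SD 25 points. Its mean without migration is 55% or 70%. Migration lowers it by d SD. All tests are two-sided at 5%.

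**Formulas.**
- Percent relief: two-sample t-test, noncentral t with n₁ + n₂ − 2 degrees of freedom and noncentrality d × √(n₁n₂/(n₁ + n₂)).
- Responders: p₀ = Φ((mean − 50)/25) and p₁ = Φ((mean − 50)/25 − d). Power is the exact sum of binomial probabilities over all tables where the uncorrected Pearson chi-square exceeds 3.84.

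**Worked case, 14 v 42, d = 0.8, mean 55%.** Noncentrality = 0.8 × √(14 × 42/56) = 2.59 on 54 degrees of freedom, so power is 72.1%. For responders, p₀ = Φ(0.20) = 0.579 and p₁ = Φ(−0.60) = 0.274, so power is 53.2%. The loss is 18.9 points.

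Power in %, with losses taken before rounding:

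| Migrated v not | d | t-test | Chi-square, mean 55% | Chi-square, mean 70% | Loss in points (55% / 70%) |
|---|---|---|---|---|---|
| 14 v 42 | 1.0 | 88.9 | 70.8 | 74.0 | 18.1 / 14.9 |
| 14 v 42 | 0.8 | 72.1 | 53.2 | 55.8 | 18.9 / 16.3 |
| 14 v 42 | 0.5 | 35.6 | 25.8 | 27.6 | 9.9 / 8.1 |
| 7 v 49 | 1.0 | 68.1 | 47.4 | 54.4 | 20.7 / 13.7 |
| 7 v 49 | 0.8 | 49.4 | 34.2 | 39.1 | 15.2 / 10.3 |
| 7 v 49 | 0.5 | 22.9 | 17.4 | 19.6 | 5.5 / 3.4 |
| 7 v 21 | 1.0 | 59.7 | 44.3 | 46.8 | 15.4 / 12.9 |
| 7 v 21 | 0.8 | 42.3 | 32.4 | 33.3 | 9.9 / 9.0 |
| 7 v 21 | 0.3 | 10.2 | 10.3 | 10.1 | −0.1 / 0.1 |
| 4 v 24 | 1.0 | 43.0 | 30.6 | 39.6 | 12.4 / 3.4 |
| 4 v 24 | 0.8 | 29.7 | 22.9 | 28.9 | 6.9 / 0.8 |

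With 7 or 14 migrated patients and d of 0.8 to 1.0, the loss runs from 9.0 to 20.7 points. At 0.3 to 0.5 SD it is about 0 to 10.

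**High migration.** The Background cites rates up to 69.2%. That gives 0.692 × 56 = 38.8, so 39 v 17. At d = 0.8 the t-test has 77.1%, against 62.3% (mean 55%) or 54.2% (mean 70%). The loss therefore does not depend on migration being uncommon.

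**Bimodal relief.** Suppose instead that relief clusters near 75% or 20% (SD 12, limited to 0–100%) and migration moves patients from the upper cluster to the lower. In 40,000 simulated studies per setting:
- 14 v 42, upper-cluster share 30% in migrated and 60% in other patients: t-test 44%, chi-square 49%.
- 7 v 21, shares 30% and 70%: t-test 42%, chi-square 49%.

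Here the responder test is ahead by about 5 to 7 points.

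**The case against.** The strongest defence is that the responder count is the right outcome for the question. The Background presents the SCS trial as a prognostic test and names false negatives as the harm of migration, so effectiveness can fairly mean pass or fail. Bimodal relief also suits that account of technical failure, and there the chi-square test does slightly better. This stands. It is a good reason to keep the responder comparison as an inferential result, and against reducing it to a descriptive count. It does not explain why the underlying percentage should go unanalysed.

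Three stronger readings are tempting, and the documents do not support them.
- A reader might infer that the plan loses a fixed amount of power, or a fixed share of its information. Every input on pain relief is an assumption, and the loss ranges from sizeable to negative.
- A reader might infer that the plan rules out analysing percent relief. No sentence ties the chi-square test to Objective 1 by name, and the regression and catch-all sentences leave room. The gap is an unspecified analysis, not a prohibition.
- A reader might infer that the cut is what makes Objective 1 weak. With 7 migrated patients out of 56 and a 0.8 SD effect, even the t-test has only 49% power. Patient-level migration is also undefined when one of two leads moves, and migration itself is not randomised. These limits apply on either scale.

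**Conclusion.** The point holds as a cheap improvement to a secondary objective. The documents settle three things: the only effectiveness outcome for Objective 1 is a yes/no count, proportions go to chi-square, and no analysis of percent relief is specified.

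The size is conditional. The loss is about 9 to 21 points if relief is roughly normal (SD 25, mean 55% to 70%), migration costs 0.8 to 1.0 SD, and 7 to 14 patients out of 28 or 56 migrate. It is about 0 to 10 points at 0.3 to 0.5 SD. With 4 v 24 patients and mean relief of 70% it is near zero up to 0.8 SD. If relief is strongly bimodal, the sign reverses slightly. Since the shape of relief is unknown in advance, planning both analyses is safer than relying on either alone.

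**What to change.** Record percent pain relief as a number for every patient. Add to the Analytical Plan a comparison of percent relief by migration: either the mean difference between patients with and without migration, or the slope on millimetres of migration, with a 95% CI. Report it beside the responder comparison, which stays as the clinical pass/fail result. State in advance which of the two is the main test of Objective 1, and how a patient with one migrated lead is classed, since either analysis needs that.

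The cost is one numeric field on the data form, a few lines of plan text and a second secondary analysis, which is why the main test must be named beforehand. Sample size and conduct do not change. The change will not make Objective 1 well powered, so the CI should carry the interpretation and a non-significant result should not be read as no effect.
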